5.7.5. Additional Medical Concerns (Safety). Adverse events (AEs) and Serious Adverse Events (SAEs) will be tracked monthly at each follow-up appointment. In addition, in cases where participants have elevated liver enzymes and will be discontinued on XR-NTX, they will be linked with follow-up medical services to monitor liver function. All participants requiring additional medical or psychiatric care will be monitored and

followed up and be referred for additional care on a case-by-case basis. All participants are under the care of the study physician and GLC and will be monitored monthly through treatment phases. Where further medical treatment is required, appropriate referrals and consultation will be ongoing. Our study physician will follow the recommendations in the SAMHSA (2015) Clinical Use of Extended-Release Injectable Naltrexone in the Treatment of opioid Use Disorder: A Brief Guide by referring a patient for more intensive or specialized care.

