5.8.5. Opioid Overdose Scale. This self-administered questionnaire will ask participants to report the number of opiate overdoses where they did and did not receive medical attention. The questionnaire administered at baseline will cover the period prior to the instant incarceration while the questionnaire follow-up in the community, will cover post-release months 1-12.

5.8.6. Visual Analogue Scale (VAS). Participants are asked to place a mark across the line at the point that corresponds to their immediate craving for opioids. Anchors included 0 mm – ‘no cravings’ to 100 mm – ‘most

extreme cravings possible'.^{94,95} Participants will be assessed at baseline and at each follow-up visit and asked about peak cravings during the preceding 24 hours.

5.8.7. Health-related quality of life will be measured by the EuroQol 5D (EQ-5D).^{108, 109} The preference weights obtained from the EQ-5D will be used to calculate quality-adjusted life-years (QALYs; see section D.4). The EQ-5D is the most widely used generic, preference-based health-related quality of life instrument.¹¹⁰

5.8.8. Official Records. As in our previous research,⁹⁶ official record data will be obtained from the MDPSCS at 12-months. Data will include type (e.g., charges involved) and number of arrests, convictions, and incarcerations; and the number and length of time of each imposed disciplinary period. Criminal record data will be used to assess the validity of self-report criminal activity data.

5.8.9. Biometric Measures. All participants will complete the following biometric measures for inclusion/exclusion criteria, participant monitoring, and serious adverse event (SAE) and adverse event (AE) reporting. The following biometric measures will be completed (see **Figure 3**): 1) history and physical; 2) liver function tests (note: if a blood specimen is unable to be drawn the individual will not be excluded from participation), hepatitis profile; 3) vital signs; 4) concomitant medications; 5) pregnancy, 6) HIV; 7) Urine toxicology; and 8) AEs.

5.8.10. Data Management/Quality Control. Assessments will be administered by trained RAs, and closely supervised by the PI. RAs will receive training concerning: (a) initiating and developing rapport; (b) sensitivity regarding culture, gender, and sexual orientation; (c) forms administration; (d) serious adverse event reporting; (e) responsibility for maintaining participant confidentiality; and (f) follow-up procedures.

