5.9. Study Aims, Hypothesis, Rationale

5.9.1. Aims. The proposed study has two specific aims: **Aim 1.** To compare the two study conditions in terms of: a) XR-NTX treatment adherence; b) opioid use; c) criminal activity; d) re-arrest; e) re-incarceration; and f) HIV risk-behaviors (i. needle use; ii. risky sexual behaviors). **Aim 2.** To determine if the number of months of post-release XR-NTX treatment is related to outcome (a-f above), and if so, is there a point at which XR-NTX v. Non-XR-NTX equilibrates.

5.9.2. Hypothesis. Based on data from the research team's current studies (see above), It is anticipated that the XR-NTX+MMTx condition will have superior outcomes compared to the XR-NTX+OTx condition in terms of outcomes (a)-(f).

5.9.3. Rationale. We are not aware of RCTs using mobile medical treatment for the provision of XR-NTX. However, based on studies utilizing mobile treatment for HIV services, and methadone, which increased access, engagement, and retention, we believe the provision of medical treatment, provided at a participant's place of residence, is expected to yield better adherence, subsequently, improving outcomes mentioned above. If we find a point of equilibration it will tell us how many months we will need to provide mobile treatment (XR-NTX) and at what point it impacts on outcomes-significant given the cost of the medication. It is difficult to provide firm conjectures on this latter question given the lack of research in this area.

Figure 2: Data Collection Schedule

Measures	Source	Interval	Operational Definition
Aim 1: Outcomes (a)-(f)			
a. XR-NTX adherence	Clinic records	B, 1-6	• # of injections due/completed
b. opioid use	ASI/TLFB/UDS	B, 1-6, 7, 12	• days of opioid use • positive opioid urine drug screen
c. criminal activity	ASI/TLFB	B, 1-6, 7,12	• days of crime
d. re-arrest	Official records	12	• time to re-arrest
e. re-incarceration	Official records	12	• time to re-incarceration
f. HIV risk behaviors	RAB/TLFB	B, 1-6, 7,12	• scored 0-22 (higher risk) • scored 0-18 (higher risk)
i. needle use			
ii. risky sex behaviors			
Aim 2: Outcomes (a)-(f)			
(a)-(f) equilibrates	Above	1-6,12	Time to relapse
Supplementary			
other treatment	ASI	B, 1-6, 7, 12	• Days in other treatment
opioid overdose	OOS	B, 1-6, 7, 12	• # of times overdosed
opioid craving	VAS	B, 1-6, 7, 12	• 0-100 (higher cravings)
Quality of Life	QOL	B, 1-6, 7, 12	

Figure 3: Biometric Measures

Measures	Data Collection Point						

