
6.8. Supplementary Analyses. We will tabulate (and test for treatment condition differences) for the relative frequency of each adverse event (AE) in each condition, where the examination is based on the proportion of

individuals who experience the AE, and the number of that AE reported. In addition, we will tabulate and test for treatment condition differences) for the relative frequency of opioid overdoses in each condition, where the examination is based on the proportion of individuals who report overdoses during the 12-months post-release. We will also calculate mean scores of cravings at each follow-up.

6.9. Additional Process Data *We will collect three additional process variables: (1) data on housing stability at each follow-up visit that will utilize a checklist to describe the participant's place of residence and the level of stability; (2) data on the distance travelled from place of residence to Glenwood Life Counseling Center (GLC) for participants randomized to TAU; and (3) data on the number of counseling sessions received during the course of the study (this will account for any community counseling received during treatment).*

6.10. Follow-up Analyses. *Follow-up analyses will include select covariates in the model, with a focus on the covariate X BI Intervention Condition (X Time, if an outcome is measured repeatedly). These follow-up analyses can be viewed as either sensitivity analyses or as subgroup analyses^{106,107} intended to map the population(s) for which the intervention is maximally useful and/or examine the robustness of the findings under uncertainty in the model. Possible covariates include: (1) crime severity, (2) opioid severity, (3) housing stability, (4) distance travelled from place of residence to treatment clinic; and (5) number of counseling sessions received.*

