9.1. Potential Risks

9.1.1. Extended-Release Naltrexone (XR-NTX). Participants may experience brief withdrawal symptoms with the naloxone test, although this will be uncommon as only patients with a history of no opiate use and negative urine for opiates will be given the test. Those receiving an XR-NTX intramuscular injection may experience side effects consisting of pain at the site of injection, nausea, or other opioid withdrawal symptoms. In rare cases, an infection at the site of injection has occurred. XR-NTX has been reported to cause increased liver enzymes when it was given in high dose oral form, but this has not been reported with the dose used in the injection. Participants in both conditions carry the risk of relapse to opioid dependence, as is the case for all individuals who have a history of opioid use disorder. Relapse to opioid dependence after a detoxification and opioid-free period, or after discontinuing depot naltrexone, carries a risk of opioid overdose and death because tolerance after a period of abstinence is low. Participants will be informed of these risks and of treatment alternatives, including agonist maintenance.

XR-NTX injections will block the effects of opioid pain medication and all participants randomized to the naltrexone condition will receive a card to present in case of emergency need for opioid analgesia. General anesthetics, nerve blocks, and non-steroidal pain medications are not affected. All individuals who will be administered depot naltrexone will be informed as follows: **“You should carry identification to alert medical personnel to the fact that you are taking depot naltrexone. A depot naltrexone medication card has been supplied to you for this purpose. Carrying the identification card should help to ensure that you can obtain adequate treatment in an emergency. If you require medical treatment, be sure to tell the treating physician that you are receiving depot naltrexone therapy”**.

9.1.2. Other Risks. Other risks are expected to be minimal. Participants will be asked to provide sensitive information regarding a number of behaviors, including deviant and criminal behaviors, and are thus exposed to the risks associated with the potential for disclosure of confidential information outside the research context. Because participants will be discussing personal information, including information on psychological functioning, some participants may experience emotional discomfort.

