9.8. Adverse Event Reporting

As in our other clinical trials, adverse event reporting will follow the usual FRI policy. Serious adverse events (SAEs) include any of the following outcomes for the participant: 1) death; 2) acute life-threatening incidents; 3) hospitalization or the prolongation of a hospitalization; 4) persistent or significant disability or incapacity; or, 5) birth defects. Should they occur, these events may be communicated to the PI by participants and/or staff, or may be observed directly by the PI. SAEs will be reported regardless of whether they are considered study related. Adverse events will be monitored by nursing and medical staff and will include: nasopharyngitis, insomnia, and injection site pain among other more frequently reported reactions. The completed Serious Adverse Event Form will contain: subject's ID#, gender, age, the title and date of the Serious Adverse Event, and narrative explanation. The Serious Adverse Event Report Form tracks how the research staff was notified of the event, dates of consent, study medication, study screening for inclusion/exclusion, study treatment received, outcome of study treatment (e.g., was participant using illicit substances or abstinent, other relevant clinical information), dates and circumstances of the hospitalization/death, whether alcohol or illicit substances were known to be involved, and participant status at last clinical or research contact. In cases of participant death, the report also includes appropriate substantiation from clinic records, as well as copies of the death certificate, autopsy report, or medical record. The Principal Investigator will address whether there is a need to redesign or amend the protocol, and/or to inform current and future subjects of a change in description of risk (in consent form and protocol or other). The Principal Investigator will state whether the event was "expected" and assess its "relatedness" to the study medication or intervention.

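### The 12-month overdose comparison counts only self-reported overdoses, so a fatal overdose in someone with no earlier report is counted as no overdose or dropped

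*Combined protocol and SAP*

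**What the plan says.** Section 6.8 plans two between-arm safety comparisons.

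- **Overdose.** It is tabulated and tested by arm, where "the examination is based on the proportion of individuals who report overdoses during the 12-months post-release".
- **Adverse events.** Each is tabulated and tested on the proportion of "individuals who experience the AE, and the number of that AE reported". Neither overdose nor death is named here.

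Section 5.8.5 describes the overdose instrument: "This self-administered questionnaire will ask participants to report the number of opiate overdoses where they did and did not receive medical attention". The follow-up version "will cover post-release months 1-12". Figure 2 (section 5.9) places overdose among the supplementary measures, gives the OOS as its only source, schedules it at baseline and months 1-6, 7 and 12, and defines it as the number "of times overdosed".

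Deaths are handled elsewhere. Section 9.8 makes death an SAE, reportable whether or not it is study related, and the report on a death includes substantiation from clinic records, "as well as copies of the death certificate, autopsy report, or medical record". Section 9.10 carries reporting of unexpected SAEs through the follow-up period, and under section 9.12 the DSMB reviews all SAEs. Section 5.7.5 says that AEs and SAEs "will be tracked monthly at each follow-up appointment"; the AE row of Figure 3 ends at month 6/7.

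Section 6.2 defines the intent-to-treat population as everyone consented and randomised, analysed on available data. Section 9.1.1 warns that relapse, or stopping depot naltrexone, "carries a risk of opioid overdose and death because tolerance after a period of abstinence is low".

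**The concern.** The outcome is defined by the act of reporting, and the gravest form of the event removes the person who would report it. Nothing in sections 5.8.5, 5.9, 6.2, 6.6 or 6.8 says how a participant who dies is classified. Section 6.6 does not fill the gap: a documented death from overdose is an observed event, not a missing questionnaire.

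The omission cannot be assumed equal between arms. Section 5.9.2 hypothesises better adherence with mobile delivery, and section 9.1.1 ties the risk of overdose death to stopping the drug. If adherence differs as hoped, exposure to that risk may differ too. Section 8.0 also lists fewer overdose deaths among the hoped-for effects, yet the one analysis that names overdose cannot count such a death. At stake are the direction and size of a safety estimate.

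**Working it through.** The plan gives no overdose rate and no power for this comparison, so there is no stated figure to reproduce. The check concerns the outcome definition, with assumed counts to show its effect.

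**Inputs from the documents.** 120 per arm (section 5.4); about 10% lost at month 12, 240 × 0.9 = 216 (section 6.7), or 108 per arm if the loss is equal; OOS as sole source (Figure 2).

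**Assumed inputs.** Per arm, 6 to 12 participants self-report an overdose, and 0 to 8 die of overdose with no earlier report.

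**Step 1: effect of one death.** Let *a* be the self-reporters and *f* the overdose deaths without an earlier report.

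- Counting every overdose: (a + f)/120.
- As planned, with the dead kept in the denominator: a/120. The shortfall is f/120, so one death costs 1/120 = 0.83 percentage points.
- As planned, with the dead dropped: a/(120 − f). For a = 8 and f = 5 this is 8/115 = 7.0%, against 13/120 = 10.8%. The shortfall is 3.9 points, or 0.78 per death.

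Section 6.8 does not say which denominator applies. Both understate.

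**Step 2: when the direction reverses.** With the dead kept in the denominator, suppose arm A has fewer reporters than arm B (a < b). The order reverses once deaths are counted if f_A − f_B > b − a, that is, if A's excess of unreported deaths exceeds its deficit of reporters.

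**Step 3: illustrations** (reporters + unreported deaths, 120 per arm, Fisher exact p).

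| A v. B | Self-report only | Any overdose |
|---|---|---|
| 10+2 v. 10+0 | 8.3% v. 8.3%, p = 1.00 | 10.0% v. 8.3%, p = 0.82 |
| 8+3 v. 10+0 | 6.7% v. 8.3%, p = 0.81 | 9.2% v. 8.3%, p = 1.00 |
| 8+5 v. 10+1 | 6.7% v. 8.3%, p = 0.81 | 10.8% v. 9.2%, p = 0.83 |
| 6+6 v. 10+1 | 5.0% v. 8.3%, p = 0.44 | 10.0% v. 9.2%, p = 1.00 |
| 6+8 v. 12+0 | 5.0% v. 10.0%, p = 0.22 | 11.7% v. 10.0%, p = 0.84 |

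The last four rows reverse. In the third row, for example, the excess of deaths is 5 − 1 = 4 and the deficit of reporters is 10 − 8 = 2.

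**Step 4: choice of denominator.** For 8+5 v. 10+1, self-report among survivors gives 8/115 = 7.0% v. 10/119 = 8.4%. With 108 assessed per arm it gives 8/108 = 7.4% v. 10/108 = 9.3%. Arm A looks safer each time, so the reversal does not depend on the denominator.

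**The case against.** A reader might infer that fatal overdoses escape the trial altogether. They do not. They are SAEs with documentary substantiation, the DSMB sees all SAEs, and section 9.13.1 has it weigh fatal events when it considers stopping.

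A reader might also infer that the AE tabulation cannot contain these deaths because the AE row of Figure 3 stops at month 6/7. The documents do not support that. Figure 3 is a schedule of biometric measures at visits, not a cut-off for SAE reporting, and section 9.10 extends reporting of unexpected SAEs through follow-up. The AE comparison counts people who experience an event, so a fatal overdose coded as an AE could be tested by arm there. What remains is that the plan does not say so, and the overdose proportion would still exclude that death.

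Three further points stand. The OOS is given repeatedly, so someone who reported a non-fatal overdose before dying still counts as a reporter. Overdose is a supplementary outcome, not one of Aim 1 outcomes (a) to (f), and both arms receive XR-NTX. The counts above are assumed and no comparison in the table is statistically significant; the only overdose occurrence that section 1.0 reports from the pilot is none in the first month after release among 27 participants. These points limit the size and importance of the concern. They do not change how an unreported fatal overdose is classified.

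**Conclusion.** The concern holds for the overdose comparison in section 6.8, and only there. As written, a fatal overdose in a participant with no earlier report is counted as no overdose or dropped. The arm's proportion is understated by 0.83 percentage points per death if the denominator stays at 120, and by slightly less per death (0.78 in the worked case) if the dead are dropped.

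A modest imbalance in such deaths could reverse the apparent direction. It is tempting to conclude that the arm with more deaths will look safer, or that a test result would change. Neither follows. Reversal needs the excess of unreported deaths to exceed the deficit of reporters, and at the assumed counts p lies between 0.22 and 1.00 under either definition. The defect is a bias in a supplementary safety estimate. It is worth correcting because the source data are already required and the event is one the protocol itself warns about.

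**What to change.** In section 6.8, define the outcome as any opioid overdose, fatal or non-fatal, within 12 months of release. Take non-fatal events from the OOS and fatal events from the SAE death documentation required in section 9.8, and amend the Figure 2 source to match. State that deaths are recorded to month 12, since the explicit wording on the follow-up period in section 9.10 concerns unexpected events.

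Keep the section 6.2 population of all randomised participants. Count each overdose death as an event. Handle survivors with missing OOS data by the section 6.6 approach: a plain all-randomised denominator would silently treat the roughly 10% expected to be lost by month 12 as having had no overdose. Limiting the denominator to participants actually released would depart from section 6.2.

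Beneath the combined figure, show fatal overdose, non-fatal overdose and all-cause death by arm to month 12.

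The cost is SAP wording, a merge of SAE death records with the OOS data, and a rule for classifying cause of death from the certificate, autopsy report or medical record. No new visit or instrument is needed. One limit remains: section 9.8 has SAEs reach the investigator through participants, staff or direct observation, and the official records in section 5.8.8 cover criminal justice events only, so deaths among participants lost to contact may still be missed. The report should say so.

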5.5. Participant Attrition

Consistent with our previous studies, we will collect detailed locator information that has enabled us in the past to successfully locate participants for follow-up. Thus, we anticipate follow-up rates well over 90%, which is consistent with our previous studies conducted at FRI.^{43,45-47,74,81}

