5.7. XR-NTX Treatment in the Community

5.7.1. Glenwood Life Counseling Center for XR-NTX injections. The participants randomized to XR-NTX-OTx will go to GLCC only to receive injections under the direction of [name] and the study nurse from prison in order to ensure continuity of care for those receiving XR-NTX in the community (injections will occur every 28 days). The study RA will be in close contact upon release and will provide the client with reminder calls and/or visits prior to each XR-NTX appointment. Prior to each injection (at GLCC and place of residence), the nurse will administer: 1) a drug use questionnaire, and 2) an instant urine drug screening test. If negative for opioid use participants will be administered XR-NTX. If the participant reports using opioids in the past 7-10 days or tests positive on the urine drug screen they will not be administered XR-NTX (see procedures below for missed XR-NTX injections). Once the participant receives the injection, he/she will be monitored for up to 1½ hours. In addition, the nurse will provide the participant with the Naltrexone Medication Card, and tell the participant that he/she should keep it at all times. The nurse or physician will follow the same procedures as in prison.

5.7.2. Place of Residence for XR-NTX injections. For those randomized to receive XR-NTX at their place of residence, specific procedures will be implemented. First, the study nurse will be accompanied by the study RA so two staff members are always physically present. The study RA will confirm the place of residence prior to release from prison using our locator form. Contact will be made with the participant immediately following prison release and subsequently one week before each scheduled injection to verify his/her home address as

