6.4. Explanatory Variables. The predictor variables in all statistical models can be categorized as either Treatment Variables, Covariates, or Control Variables. (From a statistical viewpoint, this categorization is arbitrary and is utilized here simply for ease of presentation.)

Treatment Variables. There will be a single treatment variable: Treatment Condition (XR-NTX-MMTx v. XR-NTX+OTx).

6.4.1. Covariates. Three additional predictor variables – Age, Gender, and age of onset of criminal activity – will be included as “main effects” in all analyses. These “main effects” test for the unique contribution of each of these variables in predicting outcome, above and beyond the effects of Treatment Condition. Each of these variables, as well as its respective interaction with Treatment Condition, will be included as a predictor in order to examine for potential differences in treatment outcome as a function of each covariate, and whether any of these three covariates moderate treatment efficacy.

6.4.2. Control Variables. Finally, because participants may know one another through contact at their respective prison, it is possible that participants' responses within a given prison will not be entirely independent of each other. This potential lack of independence must be controlled for by including Prison nested within Treatment Condition and Participants nested within Prison nested with Treatment Condition as random factors. [Although neither of these two effects represents a substantive effect of interest, both must be included in order to produce unbiased estimates and tests of significance for Treatment Condition.]

6.4.3. Time. Finally, the “repeated factor” in the statistical analysis of all outcome variables measured repeatedly will be assessment Time point, which will allow for the evaluation of both *differential course and impact* of the interventions as a function of the “between-subjects” Treatment Condition factor. (For information regarding which outcome variables are measured at what assessment time points, see **Figure 2**, above.)

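### Distance to the clinic is to be collected in one arm only, yet is listed as a possible covariate for covariate-by-condition models that need it in both arms

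*Combined protocol and SAP*

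**What the plan says.** Section 6.9 (Additional Process Data) names three process variables. The second is "data on the distance travelled from place of residence to Glenwood Life Counseling Center (GLC) for participants randomized to TAU". Housing stability and counselling sessions, the other two, carry no restriction by arm.

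Section 6.10 (Follow-up Analyses) describes models that add selected covariates, "with a focus on the covariate X BI Intervention Condition (X Time, if an outcome is measured repeatedly". It presents them as sensitivity or subgroup analyses meant to show for whom the intervention is most useful. The candidates are introduced as "Possible covariates include: (1) crime severity, (2) opioid severity, (3) housing stability", and the list continues with "4) distance travelled from place of residence to treatment clinic" and the number of counselling sessions.

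Section 6.4 defines the treatment factor: "There will be a single treatment variable: Treatment Condition (XR-NTX-MMTx v. XR-NTX+OTx". Neither level is called TAU, and section 4.2 says that a treatment-as-usual comparator was considered and rejected. The arm that travels to the clinic is identified in section 5.7.1: "The participants randomized to XR-NTX-OTx will go to GLCC only to receive injections".

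On addresses, section 5.5 says "we will collect detailed locator information", without restriction by arm. Section 5.7.2, which concerns the mobile arm, says "The study RA will confirm the place of residence prior to release from prison using our locator form".

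**The concern.** A distance-by-condition term asks whether the relation between distance and outcome differs between the arms. That needs a distance for participants in each arm. Section 6.9 schedules it for one arm, so two adjacent sections cannot both be carried out as written.

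The question is close to the trial's rationale. Sections 1.0 and 8.0 justify home delivery partly by the travel time and cost that it removes. Section 5.2 admits people living outside Baltimore City and County if they agree to travel when assigned to the clinic, so distances may vary a good deal. With distance known only in XR-NTX-OTx, the trial could show whether living far away goes with poorer adherence at the clinic. It could not show whether mobile delivery flattens that gradient, which is what a moderator analysis of distance would address.

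**Working it through.** The plan gives no figure for this analysis. The power statements in section 6.7 concern Treatment Condition and Treatment Condition by Time, so there is nothing to reproduce. The question is whether the term can be estimated at all.

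**Inputs.** Two conditions with 120 participants each (synopsis; sections 5.4 and 7.0); one two-level treatment factor (6.4); distance collected in one arm (6.9); covariate-by-condition model (6.10).

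**Model.** Let C = 0 for XR-NTX-OTx and C = 1 for XR-NTX+MMTx, and let D be distance. The linear predictor is

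b0 + b1·C + b2·D + b3·C·D.

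The distance slope is b2 in the clinic arm and b2 + b3 in the mobile arm, so b3 is the moderator effect. All four coefficients are estimable only if the four columns [1, C, D, C·D] are linearly independent. I checked the rank with 120 per arm and simulated distances:

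| Distance in the mobile arm | What happens to the columns | Rank (of 4) |
|---|---|---|
| Recorded | All four independent | 4 |
| Missing, complete-case fit | Only the 120 with C = 0 remain; C and C·D are all zero | 2 |
| Set to 0 | C·D is zero for everyone | 3 |
| Set to a constant k | C·D = k·C, a multiple of the condition column | 3 |

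In each of the last three rows b3 is not identified, and b2, the slope within XR-NTX-OTx, is the only distance effect left. In the complete-case row the condition effect b1 is lost too. With zero coding, b1 can be fitted, but it compares the mobile arm with a clinic participant extrapolated to zero distance.

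**By Time.** The three-way term needs both arms' distance slopes over time, and the mobile arm again supplies none. A logit or log link does not alter the fixed-effect columns, so the binomial and Poisson outcomes are affected alike.

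**Missing-data provisions.** The flexibility described in section 6.6 concerns missing outcomes. Multiple imputation does not help here: with no observed mobile-arm distance, any imputed mobile-arm slope comes from the imputation model's assumptions and not from data.

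**After repair.** With distance in both arms the rank is 4. To show what could then be seen, I assume a normal outcome with residual SD 1, distance standardised with equal variance in both arms, two-sided alpha .05 and 80% power:

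- SE of the slope difference = √(2/n per arm).
- n = 120: SE = √(2/120) = 0.129; detectable difference = (1.960 + 0.842) × 0.129 = 0.36 SD of outcome per SD of distance.
- n = 108 (half of the 216 in section 6.7): SE = √(2/108) = 0.136; detectable difference = 0.38.

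The documents set no target for this effect. The analysis would be estimable but still exploratory.

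**The case against.** The best case on the other side is that this is a wording mismatch in optional analyses. Much of that stands.

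- *Commitment.* A reader might infer that the sponsor has committed to test distance as a moderator. Section 6.10 does not say so: covariates are selected and possible, and distance has no priority over the other four. The moderators that are committed, in section 6.4.1, are age, gender and age of onset of criminal activity.
- *Reach.* A reader might infer damage to the main results. Aims 1 and 2 do not involve distance, and the power calculation does not use it.
- *Loss of the mobile arm.* It is tempting to say that any fit would discard these participants. That follows only if the values are left missing; zero coding keeps them, though the interaction stays unidentified.
- *Irrecoverable information.* The documents do not show that the information would be lost. Mobile-arm residence is confirmed before release, and the wording in 6.10 has no arm restriction, so distance could be derived later. But no section says that it will be, and 6.9 says otherwise.
- *Addresses already held.* This too is an inference for the clinic arm. Section 5.5 does not describe what the locator information contains, and explicit confirmation of residence appears only in the mobile-arm procedures.
- *The label.* Reading TAU as XR-NTX-OTx is also an inference, though the only one that fits the text.

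Section 5.7.2 expects 4 to 6 homeless participants and allows homeless participants to be injected at the clinic or a field office. That does not supply the missing data, because 6.9 restricts collection by randomised arm.

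**Conclusion.** The point holds as an inconsistency between sections 6.9 and 6.10. If the plan is followed as written, one listed exploratory analysis cannot be done: half the sample (120 of 240) has no distance value, and the distance-by-condition term, with or without Time, is not identified under any of the codings examined. The slope within XR-NTX-OTx remains estimable and has some bearing on travel burden.

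This rests on reading TAU as the clinic arm and on taking the restriction in 6.9 literally. It does not threaten the Aim 1 or Aim 2 analyses. It still deserves a change, because the question is tied to the reason for offering mobile treatment and the repair is small.

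**What to change.** 1. In section 6.9, replace TAU with XR-NTX-OTx if that is what is meant. In 6.10, correct the condition label as well, since BI matches neither arm.
2. Record or derive, for every randomised participant in both arms, the distance from planned residence at release (locator form) to the clinic. Use this baseline value in 6.10. Preferably take the address recorded before the assignment is revealed, so that it cannot depend on the arm.
3. State how participants with no fixed planned address are handled.
4. If the sponsor prefers not to do this, remove distance from the interaction list and describe it as an analysis within XR-NTX-OTx only.

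The cost is a little geocoding and a check that the locator form captures the planned address in both arms. Distance from planned residence is not the same variable as distance actually travelled. It will carry measurement error for participants who move or are homeless, and section 5.7.2 itself notes that stable housing is often hard to obtain after release. In return it is defined alike in both arms and is unaffected by moves after release.
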